8.4. Safety Analysis

Safety and tolerability of SAGE-324 will be assessed based on TEAEs, changes from baseline in clinical laboratory evaluations, 12-lead ECGs, and vital signs, C-SSRS, PWC-20, and ESS. Safety data will be listed by participant.

For safety summary tables, the safety endpoints evaluated at scheduled visits are taken as done and nominal visit will be summarized as scheduled visits. For multiple values from the specific visit window, the choice of the visit record will be following the same rule as described in [Section 8.3.2](#).

All safety summaries will be prepared by dose level and overall for the Safety Set. See [Table 4](#) for details on how safety endpoints will be presented.

Table 4: Presentation of Safety Endpoints

Safety Evaluation	Incidence	Raw Value	Change from Baseline	Abnormality	Derived PCS values
TEAEs	X	*			
Vital Signs		X, *	X		X, *
12-lead ECG		X, *	X	X, *	X, * (QTcF only)
Safety Labs (Chemistry, Hematology, Urinalysis)		X, *	X	X, *	X, *
ESS	X	*	X		
PWC-20	X	*			
C-SSRS	X	*	X		

X = Safety Assessment will be summarized in tables
 * = Safety Assessment will be presented in individual participant data listings
 Note: PCS = Potentially Clinically Significant.

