8.4.2. Clinical Laboratory

All statistical analyses of laboratory values will be performed using SI units. The following parameters are mentioned in the protocol, hence will be summarized; any other parameters for which data are reported will be listed but not summarized.

Biochemistry:

- Renal Panel: glucose, calcium, phosphorus, blood urea nitrogen, creatinine, sodium, potassium, chloride, total carbon dioxide content
- Hepatic Panel: albumin, alanine transaminase (ALT), aspartate transaminase (AST), total bilirubin, direct bilirubin, indirect bilirubin, alkaline phosphatase, total protein, lactate dehydrogenase, gamma glutamyl transferase, creatine kinase (MB and MM)

- Other: total lipid profile, creatine phosphokinase, thyroid stimulating hormone (TSH), alcohol level, HbA1c

Coagulation:

- Activated partial thromboplastin time, prothrombin time, and international normalized ratio

Hematology:

- Red blood cell (RBC) count, hemoglobin, hematocrit, white blood cell count with differential, platelet count, and if RBC indices are abnormal, reflex RBC morphology is indicated

Urinalysis:

- Protein, glucose, pH, blood, leukocytes, leukocyte esterase, urobilinogen, bilirubin, ketones, nitrite, myoglobin

Some numeric lab values may be reported as ‘<n.n’ or ‘>n.n’; these will be analyzed in the summary statistics as n.n/2 and n.n, respectively. For example, triglycerides recorded as “<0.50” mmol/L would be analyzed as 0.25 mmol/L and potassium recorded as “>6.0 mmol/L” would be analyzed as 6.0 mmol/L.

All by-visit laboratory summary tables will present results for the Safety Set participants overall, and by dose level received prior to the given evaluation. For summarization of incidence data any time post-baseline, participant data will be summarized according to the last dose received when a particular criterion was met (thus, a participant may contribute data under more than one dose if a criterion was met post-baseline while taking different doses).

Continuous hematology, chemistry, coagulation, and urinalysis results (raw and change from baseline) will be summarized at each scheduled time point. Categorical urinalysis results will be summarized by frequencies and percentages at each scheduled time point. The number and percentage of participants with shift from baseline based on the laboratory normal ranges provided by the laboratory will be tabulated at each scheduled visit.

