Any laboratory value considered clinically significant by the investigator is captured as an adverse event.

The number and percentage of participants with potentially clinically significant (PCS) values at any time after IP administration (including unscheduled visits) will be summarized for the hematology, chemistry, and coagulation parameters defined in [Table 5](#), [Table 6](#), and [Table 7](#), respectively. PCS values for each scheduled visit and end-of-treatment and end-of-study values will also be provided. These summaries will be done using the Safety Set, overall for SAGE-324 as well as by dose level.

Liver function tests will be monitored closely; PCS values ([Table 8](#)) will be summarized using the Safety Set for incidence any time post-baseline for these PCS thresholds (for conditions involving more than one parameter, the results need to be from the same timepoint).

Chemistry, hematology, coagulation, and urinalysis data will be listed with the values outside the normal ranges and PCS criterion flagged. Blood cell morphology and microscopy test results will be listed when available but not summarized. Virus serology, pregnancy tests, and urine drugs of abuse data will be listed but not summarized.

Table 5: Potentially Clinically Significant Values for Hematology

Laboratory Parameter	Sex	Units	Criteria for PCS Values (Observed values)	
			High	Low
Hemoglobin	Male	g/L	>185	<115
	Female	g/L	>170	<100
Hematocrit	Male	Fraction of 1	>0.55	<0.385
	Female	Fraction of 1	>0.49	<0.345
Platelet count		10 ⁹ /L	>600	<125
White blood cell		10 ⁹ /L	>15	<2.5
Basophils		10 ⁹ /L	>0.5	NA
Eosinophils		10 ⁹ /L	>1.5	NA
Neutrophils		10 ⁹ /L	NA	<1.5
Lymphocytes		10 ⁹ /L	>6.0	<0.5
Monocytes		10 ⁹ /L	>1.4	NA

Table 6: Potentially Clinically Significant Values for Chemistry

Laboratory Parameter	Units	Criteria for PCS Values (Observed values)	
		High	Low
Albumin	g/L	>70	<28
Blood urea nitrogen	mmol/L	>10.71	NA
Calcium	mmol/L	>2.75	<2.0
Chloride	mmol/L	>120	<90
Creatinine	mmol/L	>3xULN or >3x Baseline	
Gamma Glutamyl Transferase		>3xULN	
Glucose	mmol/L	>13.9	<2.8
Sodium	mmol/L	>150	<132
Potassium	mmol/L	>5.4	<3.3
Protein	g/L		<45
Bicarbonate	mmol/L	>34	<18
Chloride	mmol/L	>120	<90
Phosphorus	mmol/L	>1.94	<0.61
Liver Function Tests (LFT)			
Bilirubin	μmol/L	>2xULN	
Aspartate Aminotransferase	U/L	>3xULN	
Alanine Aminotransferase	U/L	>3xULN	
Alkaline Phosphatase	U/L	>1.5xULN	

Table 7: Potentially Clinically Significant Values for Coagulation

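### Laboratory shifts are planned by scheduled visit only, so analytes without a PCS limit (chiefly lipids, TSH, HbA1c, LDH, CK/CPK and urinalysis) have no tabulated count of participants ever shifted

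*SAP*

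**What the plan says.** **Shifts.** SAP 8.4.2 plans normal-range shifts by visit: "shift from baseline based on the laboratory normal ranges provided by the laboratory will be tabulated at each scheduled visit". Appendix C lists one shift table each for chemistry (14.3.4.1.2), hematology (14.3.4.2.2), coagulation (14.3.4.3.2) and urinalysis (14.3.4.4.2). None is labelled any-time or worst-value. Protocol 13.7.2 also promises baseline to post-baseline shifts, without tying them to scheduled visits.

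**Any-time counts.** The same SAP section counts participants with PCS values "at any time after IP administration (including unscheduled visits) will be summarized for the hematology, chemistry, and coagulation parameters defined in" Tables 5, 6 and 7. Table 8 adds liver criteria at any time post-baseline.

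**Analytes to be summarized.** The lists include "Other: total lipid profile, creatine phosphokinase, thyroid stimulating hormone (TSH), alcohol level, HbA1c", "Activated partial thromboplastin time, prothrombin time, and international normalized ratio" and, for urine, "Protein, glucose, pH, blood, leukocytes, leukocyte esterase, urobilinogen, bilirubin, ketones, nitrite, myoglobin". Nothing in the first or third of these lists has a criterion in Tables 5 to 8. In the second, INR has none. LDH and CK, from the hepatic panel, have none either.

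**Visit basis.** SAP 8.4 states that "the safety endpoints evaluated at scheduled visits are taken as done and nominal visit will be summarized as scheduled visits". The rule for choosing among several values in one window is in Section 8.3.2, which is redacted in the public copy.

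**Other routes.** SAP 8.4.2 lists laboratory results with out-of-range values flagged, and treats values the investigator judges clinically significant as adverse events. It also plans by-visit frequencies for categorical urinalysis results.

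**The concern.** Change in laboratory parameters is a secondary endpoint (SAP 4.2), in a study where a participant may stay for up to about 5 years. In single-arm long-term safety data, a natural question is how many participants ever moved out of the normal range. A by-visit shift table does not answer it, because the same people or different people may be abnormal at successive visits. The any-time PCS tables answer a related question, but only for analytes with a limit.

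For analytes without one, an unscheduled result outside every visit window has no place in any shift or PCS table. Unscheduled draws are often taken because something looked wrong.

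The SAP already takes the any-time view elsewhere. Section 8.4.3 counts QTcF PCS values both by timepoint and at any time post-baseline. Section 8.4.6 (Table 14.3.4.7.3) shifts suicidal ideation from baseline to the any-time maximum.

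**Working it through.** The plan states no figure for this point, so there is nothing to reproduce. Three checks follow.

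**1. Analytes against PCS limits.** I compared the SAP 8.4.2 lists with Tables 5 to 8. The lipid profile counts as one analyte, CK (MB and MM) as one and the white-cell differential as five; total carbon dioxide is matched to bicarbonate.

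| Group | Listed | With a PCS limit | Without |
|---|---|---|---|
| Renal | 9 | 9 | none |
| Hepatic | 11 | 7 | direct bilirubin, indirect bilirubin, LDH, CK |
| Other | 5 | 0 | lipids, CPK, TSH, alcohol level, HbA1c |
| Coagulation | 3 | 2 | INR |
| Hematology | 10 | 9 | RBC count |
| Urinalysis | 11 | 0 | all 11 |
| **Total** | **49** | **27** | **22** |

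INR, RBC count and the two bilirubin fractions have close relatives with limits (PT; hemoglobin and hematocrit; total bilirubin). The substantive gap is lipids, TSH, HbA1c, LDH, CK/CPK and urinalysis.

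**2. Scheduled post-baseline laboratory timepoints** (protocol Tables 2 to 4).

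- Days 8, 15, 29, 43, 57: 5
- Weeks 12 and 24: 2
- Months 9, 12, 15, 18, 21: 5
- Months 24 to 60, every 3 months: 13
- EOT and EOS: 2

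Full 60 months: 5 + 2 + 5 + 13 + 2 = 27. Through Month 12 plus EOT and EOS: 5 + 2 + 2 + 2 = 11.

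Some analytes have fewer. HbA1c is not scheduled at Days 8 to 57, so it has at most 27 − 5 = 22 timepoints; protocol Table 4 (every other visit) and protocol 12.1.6 (every 3 months) differ on the later ones. CK and urine myoglobin are fixed only at Screening and are otherwise at the investigator's discretion.

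**3. What by-visit counts imply.** Let p be the proportion shifted at each of V visits, with everyone attending.

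- Lower bound (same people each time): p
- Upper bound (different people each time): min(1, V × p)
- Independent visits, for reference: 1 − (1 − p)^V

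The documents give no per-visit rate, so p = 1% is an assumption.

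| V | Lower | Independent | Upper |
|---|---|---|---|
| 11 | 1% | 1 − 0.99^11 = 10.5% | 11 × 1% = 11% |
| 27 | 1% | 1 − 0.99^27 = 23.8% | 27 × 1% = 27% |

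With the planned 750 participants, 1% is 7.5 people, 11% is 82.5 and 27% is 202.5. Over 27 visits the range is 2.5% to 67.5% at p = 2.5%, and 5% to 100% at p = 5%. At any of these rates the by-visit tables leave the participant count undetermined.

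**The case against.** The stated endpoint, change from baseline, is analysed: raw values, changes and shifts are all planned by visit, and neither document makes ever leaving the normal range an endpoint. That stands, and it is why this is an improvement rather than the correction of an error.

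Several stronger readings are tempting, and the documents do not support them.

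- *Unscheduled results drop out.* Not in general. They count in the any-time PCS tables for analytes with limits. For the others, a value inside a visit window might be selected under the redacted Section 8.3.2. Only values outside windows certainly miss the shift and PCS tables.
- *The ever-shifted number is lost.* It is not tabulated, but it could be tallied from the flagged listings. Values judged clinically significant also reach the adverse event tables.
- *By-visit shifts are the only categorical summary.* Not for urinalysis, where by-visit frequencies are also planned.
- *Slow metabolic or thyroid drift would be hidden.* Persistent drift keeps the same people shifted, so by-visit percentages approach the ever-shifted percentage; the mean and quartile summaries would show it too.
- *The effect is 27%.* That is an upper bound. It needs 60 months, full attendance and different people at every visit, and it does not fit HbA1c, CK or myoglobin.

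One objection limits the remedy. Ever-abnormal percentages rise with the number of draws. If 2.5% of values were out of range by chance and draws were independent, 1 − 0.975^27 = 49.5% of participants would be abnormal at least once over 27 draws, with no control arm for comparison.

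**Conclusion.** The point holds in a limited form. For analytes that SAP 8.4.2 plans to summarize without a PCS limit, no planned table gives the number of participants ever shifted after baseline. The analyte count depends on the grouping stated above, but the absence of limits for the named analytes does not.

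The size is uncertainty, not demonstrated bias: at an assumed 1% per visit and full attendance, by-visit tables are compatible with 1% to 11% ever shifted through Month 12 plus EOT and EOS. The exposure is mainly to intermittent findings and to unscheduled results outside windows. The study is descriptive and the main hepatic, renal, hematology and coagulation tests have any-time PCS counts, so the importance is modest. For those covered tests many limits lie well beyond the normal range (for example ALT above three times the upper limit), so their PCS counts do not show who ever left the normal range either.

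A separate inconsistency needs settling: SAP Table 4 marks derived PCS values for a laboratory row that includes urinalysis, while Tables 5 to 8 and Appendix C contain no urinalysis PCS criterion or display.

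**What to change.** Add to Tables 14.3.4.1.2, 14.3.4.2.2, 14.3.4.3.2 and 14.3.4.4.2 a shift from the baseline category to the worst post-baseline category, using every scheduled and unscheduled result after the first dose.

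- Numeric analytes: one block for the lowest and one for the highest post-baseline category.
- Categorical urinalysis: normal at baseline to any abnormal result, since lowest and highest do not suit results such as nitrite.
- Present overall and by dose, using the last-dose rule that SAP 8.4.2 already sets for any-time incidence.
- Show the number of post-baseline assessments, or exposure, beside each percentage, so that a high figure from many draws is not read as a drug effect.

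In the same edit, reconcile SAP Table 4 with Tables 5 to 8 and Appendix C: either define urinalysis PCS criteria and a display, or remove the PCS mark for urinalysis.

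Cost: SAP wording and extra blocks in four existing tables, with no new data. The tables become slightly longer.

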8.4.3. Electrocardiogram

All by-visit ECG summary tables will present results for Safety Set participants overall, and also by dose level received prior to the evaluation. For summarization of incidence any time post-baseline, participant data will be summarized according to the last dose received when a particular criterion was met (thus, a participant may contribute data under more than one dose if a criterion was met post-baseline while taking different doses). Last value on treatment and last value on study will be summarized under the dose level last received.

The average of any multiple values collected at one visit will be used for summarization of continuous variables, including baseline ECG values. For each ECG measurement (heart rate and PR, QRS, QT, and QTcF intervals), the observed value at each scheduled visit and change from baseline at each scheduled visit will be provided. This summary will also include last values on treatment and on study. Last value on treatment is defined as the last post-baseline value between first dose of IP (exclusive) and up to last dose of IP + 1 day (inclusive). Last value on study is defined as the last post-baseline value after the first dose of IP.

In addition, the number and percentage of participants with PCS and potentially clinically significant change (PCSC) values will be summarized by scheduled timepoint and for any time post-baseline, including last value on treatment and last value on study. Individual values of QTcF will be used for PCS determination rather than the average of multiple values collected at one visit. Potentially clinically significant values will be identified for ECG parameters as outlined in [Table 9](#).

A shift table of overall ECG interpretation from baseline to scheduled post-baseline visits will be presented for the following categories: 'Normal', 'Abnormal, Not Clinically Significant', and 'Abnormal, Clinically Significant'. The shift table will be presented by visit – overall and by dose level.

Clinically significant abnormal findings will be reported as adverse events. The average of any multiple values collected at one visit of each parameter will be included in the data listing.

Table 9: Potentially Clinically Significant Values for QTcF

Units	Criteria for PCS Values (Observed Values)		Criteria for PCSC Values (Change from Baseline)	
	High	Low	Increase	Decrease

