8.4.4. Vital Signs

All by-visit vital sign summary tables will present results for Safety Set participants overall, and also by dose level received prior to the evaluation. For summarization of incidence at any time post-baseline, participant data will be summarized according to the last dose received when a particular criterion was met (thus, a participant may contribute data under more than one dose if a criterion was met post-baseline while taking different doses).

Vital sign results (systolic and diastolic blood pressure [mmHg], pulse pressure (mmHg), body temperature [$^{\circ}$ C], heart rate [beats per minute or bpm], and respiratory rate [breaths per minute]) and changes from baseline will be summarized by scheduled visit – overall and by dose level. Pulse pressure is defined as [systolic blood pressure - diastolic blood pressure].

Potentially clinically significant values will be identified for vital sign parameters as outlined in [Table 10](#). For any post-baseline visit, potentially clinically significant values will be summarized by visit.

Any vital sign results considered clinically significant by the investigator will be captured as adverse events.

Table 10: Potentially Clinically Significant Values for Vital Sign Parameters

Vital Sign	Units	Criteria for PCS Values (Observed values)		Criteria for PCSC values (Change from Baseline values)	
		High	Low	Increase	Decrease
Heart rate (supine and standing)	Beats/min	>120	<40		
Systolic Blood Pressure (supine and standing)	mmHg	>180	<90	≥ 30	≥ 30
Diastolic Blood pressure (supine and standing)	mmHg	>110	<50	≥ 20	≥ 20
Supine - Standing Systolic Blood Pressure	mmHg	≥ 20			
Supine – Standing Diastolic Blood Pressure	mmHg	≥ 10			
Orthostatic hypotension: supine – standing SBP and DBP	mmHg	SBP ≥ 20 and DBP ≥ 10			
		SBP ≥ 20 or DBP ≥ 10			

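### Any-time counts of potentially clinically significant laboratory and liver values take no account of baseline status, so a pre-existing abnormality can be reported as on-drug incidence

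*SAP*

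**What the plan says.** **Laboratory and liver values (SAP 8.4.2).** Participants are counted if they have "potentially clinically significant (PCS) values at any time after IP administration (including unscheduled visits". On population, "These summaries will be done using the Safety Set, overall for SAGE-324 as well as by dose level". The cut-offs in Tables 5 and 6 are headed "Criteria for PCS Values (Observed values", and Tables 7 and 8 use multiples of the upper limit of normal (ULN). One laboratory criterion refers to baseline: creatinine, ">3xULN or >3x Baseline". Dose attribution reads: "For summarization of incidence data any time post-baseline, participant data will be summarized according to the last dose received when a particular criterion was met". The same sentence allows one participant to appear under several doses. The Table 8 liver summary is also described as incidence at any time after baseline.

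**Laboratory shift table (SAP 8.4.2).** The "shift from baseline based on the laboratory normal ranges provided by the laboratory will be tabulated at each scheduled visit".

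**ECG (SAP 8.4.3).** "A shift table of overall ECG interpretation from baseline to scheduled post-baseline visits will be presented". QTcF is also summarised in absolute bands and in change bands (increase of more than 30 up to 60 msec, and more than 60 msec), by visit and at any time.

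**Vital signs (SAP 8.4.4).** "For any post-baseline visit, potentially clinically significant values will be summarized by visit". Table 10 gives change criteria for supine and standing systolic and diastolic pressure, but none for heart rate or for the orthostatic rows.

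**Baseline (SAP 8.1).** The last non-missing value before the first dose, so baseline status against each criterion can be derived from data already collected.

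**The concern.** A count labelled incidence and placed under a dose will be read as what happened on the drug. Here it mixes two groups: participants who first met the criterion after dosing, and participants who met it before dosing and still do. The PCS (potentially clinically significant) tables alone cannot tell them apart.

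Three features of this study make that matter. It is single-arm, so no control rate absorbs the background. It admits people up to age 80 (Protocol 8.1) who may be on stable anti-tremor drugs (Protocol 9.2.2). Follow-up may run to about 5 years with repeated sampling, and each further sample gives a pre-existing abnormality another chance to be counted.

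The SAP handles baseline elsewhere. Adverse event tables are limited to onset at or after the first dose (8.4.1), and C-SSRS shifts use the scale's own categories (8.4.6). The laboratory PCS tables have no equivalent. At stake is the reading of secondary safety tables: background can look like a drug effect, and a modest new signal can be hidden within it.

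**Working it through.** The plan states no figure on this point, so there is nothing to reproduce. The check has three parts.

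**1. Do other planned displays separate new from pre-existing cases?**
- *Laboratory shift tables* use normal ranges at scheduled visits. Suppose ALT goes from 1.5 x ULN to above 3 x ULN in one participant and stays at 3.5 x ULN in another. Both are high-to-high, and only the first is new. Values from unscheduled visits do not enter these tables.
- *By-visit PCS counts* may show a baseline count, but they give a total per visit and do not cross-classify the same participant before and after dosing.
- *Creatinine* joins its two conditions by OR, so a participant above 3 x ULN throughout still counts.
- *ECG shift* uses the overall interpretation, not QTcF bands. The QTcF change bands do help.
- *Vital signs* have no shift table in Appendix C (only 14.3.4.6.1 and 14.3.4.6.2). Blood pressure has change criteria; heart rate and orthostatic drops do not.
- *Listings* flag laboratory PCS values but do not summarise new onset.

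**2. How often could one pre-existing case be counted?** From Protocol Tables 2 to 4, scheduled post-baseline laboratory visits over 5 years are:
- Days 8, 15, 29, 43, 57: 5
- Weeks 12 and 24: 2
- Months 9 to 60, every 3 months: 18
- EOT and EOS: 2
- Total: 5 + 2 + 18 + 2 = 27

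With evening dosing on the schedule in Protocol 7.3, the Day 8, 29, 43 and 57 samples nominally follow 15, 30, 45 and 60 mg. One stable abnormality can therefore appear in all four dose columns.

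Assume a participant who is PCS at baseline has a 10% chance per visit of meeting the criterion again, independently between visits. The chance of being counted at least once is 1 − 0.9^k:
- k = 7 (through Week 24): 52%
- k = 27 (5 years): 94%

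**3. What share of the count could be pre-existing?** Let N = 750 (SAP 5.2), b = share meeting the criterion at baseline, r = chance of meeting it again, i = new-onset proportion in the rest. The last three are assumptions.
- Count as planned = N·b·r + N·(1−b)·i
- Share pre-existing = N·b·r / count
- Treatment-emergent rate = N·(1−b)·i / N·(1−b) = i

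With r = 0.8 and i = 2%:

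| b | Pre-existing | New | Count as planned | Share pre-existing | Treatment-emergent |
|---|---|---|---|---|---|
| 1% | 750 × 0.01 × 0.8 = 6.0 | 742.5 × 0.02 = 14.85 | 20.85 (2.8%) | 29% | 2.0% |
| 3% | 750 × 0.03 × 0.8 = 18.0 | 727.5 × 0.02 = 14.55 | 32.55 (4.3%) | 55% | 2.0% |
| 5% | 750 × 0.05 × 0.8 = 30.0 | 712.5 × 0.02 = 14.25 | 44.25 (5.9%) | 68% | 2.0% |

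Over a wider grid (b from 1% to 10%, r from 0.5 to 1.0, i from 1% to 5%), the share runs from 9% to 92%. The result is driven by inputs that the documents do not give.

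**The case against.** The case on the other side has real weight.

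- *Clinically significant findings are handled as adverse events.* Laboratory, ECG and vital-sign findings judged significant by the investigator are captured as AEs, and only those with onset at or after the first dose enter the TEAE tables. This stands: the primary endpoint does not use PCS counts.
- *Change criteria exist.* A reader might infer that a long QTcF or extreme blood pressure present before Day 1 will simply read as a drug effect. The documents do not support that in full. A stable value would meet the absolute criterion but not the change criterion.
- *Vital signs are mainly by visit.* A reader might extend the any-time argument to orthostatic hypotension. SAP 8.4.4 mentions any-time incidence when assigning dose, but the sentence that specifies the PCS summary is by visit, so accumulation over 5 years is not clearly planned there. What stands is the lack of any baseline reference for the orthostatic and heart-rate rows.
- *Eligibility should lower baseline prevalence.* Inclusion criterion 3 asks for good health without relevant ECG or laboratory findings. It rests on investigator judgement and sets no numeric limits tied to Tables 5 to 8, so it reduces the problem without removing it.
- *The SAP never calls these counts treatment-emergent*, and its Table 4 lists laboratory values under derived PCS values, not incidence. The text of 8.4.2 nevertheless uses the word incidence and attributes each count to a dose.

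A reader might also infer rates two to four times too high. That follows only with 5% to 15% prevalence, 5% new onset and full recurrence (0.05 + 0.05 × 0.95 = 9.8%, up to 0.15 + 0.05 × 0.85 = 19.2%, against 5.0%). None of these inputs is in the documents, and full recurrence is the extreme case.

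**Conclusion.** The concern holds as an omission in SAP 8.4.2. Laboratory and liver PCS counts are any-time, cover the whole Safety Set, are attributed to dose and called incidence, and carry no condition on baseline. The planned shift tables and listings do not fill the gap. It extends to the orthostatic and heart-rate rows of Table 10, and in weaker form to the absolute QTcF bands.

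Its size is unknown. The 29% to 68% range is an illustration that depends on assumed prevalence, recurrence and new onset. The documents do not support saying that nearly every participant with a baseline abnormality will be counted: that needs both long follow-up and recurrence. Nor is there an express rule to include such participants; the SAP is silent. The change is worth making because it is cheap and lets a single-arm safety study distinguish new from pre-existing abnormalities. It does not touch the primary endpoint.

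**What to change.** **SAP 8.4.2.** Define treatment-emergent PCS as the criterion met at any post-baseline time and not met at baseline. The denominator is participants who did not meet it at baseline and have at least one post-baseline value. Apply it separately to high and low criteria. Report it beside the existing any-time counts for chemistry, liver tests, hematology and coagulation (Tables 14.3.4.1.3, 14.3.4.1.4, 14.3.4.2.3, 14.3.4.3.3).

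**SAP 8.4.3.** Do the same for the absolute QTcF bands (14.3.4.5.3), where not met at baseline should mean neither that band nor a higher one. State whether baseline status uses the averaged or the individual value, since the section averages multiple readings for baseline but uses individual values for PCS.

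**SAP 8.4.4.** Add an any-time treatment-emergent row for the orthostatic and heart-rate criteria (14.3.4.6.2), and say which of the triplicate Day 1 readings decides baseline status.

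Keep the all-participant counts, above all for liver tests. Participants come from earlier SAGE-324 studies, so baseline may not be drug-free and a baseline abnormality is not necessarily unrelated to the drug.

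**Cost.** SAP wording and one column or row per PCS table, with no new data. The drawback is a denominator that differs by parameter, so each table must show it.
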